## 10.5. Primary efficacy analysis

The primary efficacy analysis is the comparison of the mean change from baseline to 24 weeks in the primary efficacy variable (natural logarithm of the mean over the 24-hour SDS profile for the natural logarithm of 17-OHP) between the Chronocort® treatment group and the standard therapy treatment group within the efficacy evaluable analysis set. The calculation of the primary efficacy variable is described 9.2.2. The comparison will be performed using an ANCOVA linear model as described in 8.2. The unadjusted mean of the primary efficacy variable will be presented along with the least squares (LS) estimated mean. The difference in LS means will be presented with the associated 95% two-sided confidence interval and p-value. Residual plots of scaled residuals will be used to check the fit of the model and assess whether there is any evidence of non-normality.

Summary statistics will be produced for the absolute values and change from baseline at each visit (weeks 4, 12 and 24) for the primary efficacy variable by treatment group and pre-baseline standard therapy. The geometric mean of the 17-OHP concentration will be plotted along with the 95% confidence intervals at each time point over the 24hr sampling period (15:00h to 15:00h) for each treatment group and pre-baseline standard therapy for week 24 for the primary analysis. The plot will be repeated for the baseline, week 4 and week 12 visits as part of the exploratory analyses.

Three subject profile plots will be created for each subject displaying the following results over the 24hr sampling period (15:00h to 15:00h) for week 24: 17-OHP concentration-time (on a logarithmic scale) and absolute (unsigned) deviations from the “normal” mean (SDS score) (See 9.2.2). The two subject profiles will be repeated for the baseline, week 4 and week 12 visits as part of the exploratory analyses.

All summary tables and plots above will be repeated for A4 for the secondary hormonal profile analysis.

The above analyses will be repeated in the full analysis set as part of the secondary analyses.

## 10.6. Secondary efficacy analyses

### 10.6.1. Secondary hormonal profile analysis

There will be a comparison of the mean change from baseline to 24 weeks in the natural logarithm of the mean over the 24-hour SDS profile for the natural logarithm of A4 between the Chronocort® treatment group and the standard therapy treatment group within the efficacy evaluable analysis set. The comparison will be performed using an ANCOVA linear model as described in 8.2. The same summary statistics will be produced for A4 as the primary efficacy analysis (see 10.5).

This analysis will be repeated for each of the individual baseline treatment strata for both 17-OHP and A4.

A responder analysis to compare the response between the Chronocort® treatment group and the standard therapy treatment group within the efficacy evaluable analysis set will be performed using logistic regression with adjustment for pre-baseline standard therapy. A subject will be considered a responder if their 09:00h result at week 24 is in the optimal and reference ranges as defined in Table 7. The number and percentage of subjects with a response will be presented together with the

adjusted response rate and the odds ratio will be estimated together with two-sided confidence interval and p-value.

Summary Statistics will be produced for the 09:00h result at week 24.

*Table 7: Optimal and reference ranges for responder analysis*

17-OHP	1.2- 36.4 nmol/L
Androstenedione (A4)	Males: 1.4 – 5.2 nmol/L Females: 1.0 – 7.0 nmol/L

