- No dose adjustments outside of the protocol-defined dose adjustments should be conducted, unless clinical signs and symptoms indicate an immediate need. In such cases the Sponsor’s medical monitor must be contacted (preferably before any dose changes are implemented). Any such unscheduled dose adjustments should be based on clinical symptoms only, with repeated androgen testing discouraged and must be pre-approved by the Sponsor’s medical monitor. The rationale for any dose adjustment, by both the independent blinded physician and also any changes made by the local investigator, will be recorded in the electronic case report form (eCRF).
- In subjects who have undetectable androgens at baseline on their regular medication, caution will be taken over dose reduction so as to avoid the risk of suppressed pituitary-adrenal axis occurring in these subjects.

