### 11.1.2 Visit 1 (Baseline Visit)

#### Day 1

Subjects will attend the clinic on the morning of Day 1 and must be prepared for an overnight stay. The following assessments will be carried out and recorded:

- Check of inclusion/exclusion criteria
- Subjects will asked about any AEs and concomitant medications changes since the last visit
- Record the time and dose of the last glucocorticoid medication taken prior to attending for this visit
- An abbreviated physical examination, if indicated by AEs
- Vital signs
- DEXA scan (except Germany) – this needs to be performed at Baseline Visit or within 2 weeks prior to Baseline Visit, after inclusion/exclusion criteria are checked

If the subject meets all the study criteria and they have been receiving their normal medication for the previous 5 days (i.e. sick days rules have not been applied in the preceding 5 days) they

will then be admitted to the clinic for their first 24-hour endocrine profile (17-OHP and A4). If sick day rules have been applied in the previous 5 days then the 24-hour profiling should be postponed until subjects have been receiving their normal medication for 5 days. The 24-hour endocrine profile sampling will commence at 15:00 hours on Day 1 followed by 2-hourly serum samples, hence 13 samples will be taken; 15:00, 17:00, 19:00, 21:00, 23:00, 01:00 (Day 2), 03:00, 05:00, 07:00, 09:00, 11:00, 13:00, 15:00h. These blood samples are to be taken within  $\pm 10$  minutes of the stated timepoints.

## Day 2

On the second morning of Visit 1, the following assessments will be conducted (the fasting samples to be taken at 07:00hrs):

- AEs
- Signs and symptoms of adrenal insufficiency
- The following questionnaires will be completed: MAF, SF-36® and EQ-5D™
- Waist circumference will be measured, together with weight, and the BMI calculated
- Vital signs
- ECG
- Urinalysis (including urine pregnancy test for females of childbearing age)
- Blood sample for fasting osteocalcin and CTX, insulin, glucose, HbA1c, lipids, hsCRP and total testosterone
- Blood samples will be taken for routine biochemistry and haematology
- Sample taken for PRA after the subject has been supine for 30 minutes

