### 8.2. Standard comparison methods

In general, continuous variables will be compared across treatment groups using a Normal analysis of covariance (ANCOVA) linear model including pre-baseline standard therapy and, if appropriate, the baseline assessment of the variable as covariates in the model. In the case of change-from-baseline variables, baseline will always be included as a covariate.

Binary variables, such as response, will be compared using logistic regression with adjustment for covariates as in the continuous data case.

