### 9.2.2. Derivations of SDS scores

The primary efficacy variable is the natural logarithm of the mean of the 24-hour hormonal profile of the SDS for the natural logarithm of 17-OHP. The primary analysis is focused on the change from baseline to week 24 in the primary efficacy variable.

The SDS is defined as the absolute (unsigned) number of standard deviations above or below the average of the lower and upper limit of normal.

The change from baseline to week 24 in the primary efficacy variable will be calculated in the following way:

- **Step 1: Calculate the SDS profile of log-transformed 17-OHP**

For each of the 13 concentrations at each visit (baseline, week 24), take the natural logarithm and then calculate the SDS by counting the number of standard deviations (given in Table 3) which are above or below the mean of the log transformed range (given in Table 3).

- **Step 2: Calculate the mean of the SDS profile**

Calculate the arithmetic mean over all 24-hour SDSs at each visit with the first and last observations weighted one half relative to the intermediate observations, e.g. for 13 observations ( $n_1, \dots, n_{13}$ ) this is calculated by  $(\frac{1}{2}n_1+n_2+\dots+n_{12}+\frac{1}{2}n_{13})/12$ . Lower values of the mean of the SDS profile should be interpreted as “better” hormonal control.

- **Step 3: Change from baseline to 24 weeks**

Take the natural logarithm of the mean of the SDS profile for the week 24 visit and subtract the natural logarithm of the mean of the SDS profile for the baseline visit. Negative values of this result should be interpreted as an improvement in hormonal control compared with baseline.

Table 2: Normal reference ranges for 17-OHP and A4

	Male	Female
17 OHP	1.2* – 6.7 nmol/L	1.2* – 8.6 nmol/L
A4	1.4 - 5.2 nmol/L	1.0 – 7 nmol/L

Source: Mayo Clinic.

17-OHP: <http://www.mayomedicallaboratories.com/test-catalog/Clinical+and+Interpretive/9231>.

Please note the upper reference range for females is during the Luteal phase.

\*There is no lower reference range available for 17-OHP, hence the lower limit of the optimal range (provided in Table 7) will be used in the derivation of the average SDS score. This will enable calculation of an 'unsigned' SDS score which can be used to assess potential overtreatment as well as undertreatment.

A4: <http://www.mayomedicallaboratories.com/test-catalog/Clinical+and+Interpretive/9709>

Table 3: Mean and SD of normal log-transformed range

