Analyte	Sex	mean of log e -transformed range [ log e (nmol/L) ]	SD of log e -transformed range [ log e (nmol/L) ]
17-OHP	Male	1.042	0.430
	Female	1.167	0.492
A4	Male	0.993	0.328
	Female	0.973	0.486

Source: Mayo Clinic.

17-OHP: <http://www.mayomedicallaboratories.com/test-catalog/Clinical+and+Interpretive/9231>.

Please note the upper reference range for females is during the Luteal phase.

A4: <http://www.mayomedicallaboratories.com/test-catalog/Clinical+and+Interpretive/9709>

The mean of the "normal" log-transformed range was calculated by taking the natural logarithm of the upper and lower limit given in Table 2, calculating the range of the log-transformed values and finding the midpoint of the range. The SD of the log-transformed range was approximated by dividing the range of the log-transformed values by four.

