#### 9.3.3. Methods for handling out-of-window observations

Missing 17-OHP and A4 values will be handled as follows:

- If the Day 1 15:00 sample of a 24-hour profile is completely missing, the result from the 17:00 planned time point will be used.
- If the Day 2 15:00 sample of a 24-hour profile is completely missing, the result from the 13:00 planned time point will be used.

- For all other time points where the result is completely missing, the average of the two closest results will be calculated and used for the missing time point.
- If the result at any time point is below the lower limit of quantification (LLOQ), a value of half the LLOQ will be substituted.
- For the purpose of analysis, a result will be considered to be out-of-window if more than +/-60 minutes from the scheduled time point. For each time point where the result is 'out-of-window':
  - If the out-of-window result is >60 minutes after the scheduled time point then the average of the previous scheduled time point and the out-of-window result will be calculated and used for the scheduled time point with the out-of-window result.
  - If the out-of-window result is >60 minutes before the scheduled time point then the average of the next scheduled time point and the out-of-window result will be calculated and used for the scheduled time point with the out-of-window result.

Subjects with 2 or more of the expected results missing (or outside of a +/-15 minute window) for a particular 24hr period were discussed on a case-by-case basis at the Data Review Meeting which occurred prior to database lock and study unblinding.

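### The 09:00 responder model adjusts for prior therapy only; adding the baseline 09:00 value already collected is a cheap, optional way to gain some power, though the gain may be nil

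*SAP*

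**What the plan says.** SAP 10.6.1 defines a responder by the single 09:00 result at week 24 falling inside the Table 7 range, and compares arms by "logistic regression with adjustment for pre-baseline standard therapy". No other covariate is named.

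The general rule in SAP 8.2, repeated in Protocol 13.1.3, describes the continuous model as "including pre-baseline standard therapy and, if appropriate, the baseline assessment of the variable as covariates in the model". It then says: "Binary variables, such as response, will be compared using logistic regression with adjustment for covariates as in the continuous data case". Baseline is compulsory only for change-from-baseline variables.

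The baseline 09:00 value is available. Protocol 11.1.2 schedules it within the Visit 1 profile: "hence 13 samples will be taken; 15:00, 17:00, 19:00, 21:00, 23:00, 01:00 (Day 2), 03:00, 05:00, 07:00, 09:00".

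Protocol 13.10 includes in the masked Data Review Meeting's terms of reference a review of whether further covariates are needed, and allows the SAP to be revised as a result. SAP 4.1 adopts those terms. SAP 2.3.3 treats all secondary endpoints as support for the primary analysis.

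**The concern.** The primary analysis, the A4 profile analysis and the DEXA analyses all use change from baseline, so SAP 8.2 adjusts each of them for baseline. The responder comparison is the one secondary treatment test without it, and no reason is given. Dichotomising a single sample per subject already discards information. If a subject's 09:00 value at entry predicts the value at week 24, leaving it out costs some power and leaves a chance baseline imbalance unadjusted. What is at stake is the precision of a supportive result, not the primary conclusion.

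**Working it through.** **The plan's own figure.** The only stated power is for the primary endpoint (SAP 5): 102 evaluable, falls of 0.78 and 0.2, SD 0.681, two-sided 5%. With 51 per arm (1:1 is assumed; the ratio is not stated):

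- z = 0.58 / (0.681 × √(2/51)) = 0.58 / 0.1349 = 4.30
- power = Φ(4.30 − 1.96) = 99.0%, consistent with the stated figure of above 95%
- 102 / 0.85 = 120 randomised, as stated.

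No power is given for the responder test.

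**Responder test without baseline.** Assume 50% v 70% response, 51 per arm. The normal approximation gives Φ[(0.20 × √51 − 1.96 × √(2 × 0.6 × 0.4)) / √(0.25 + 0.21)] = Φ(0.0704 / 0.678) = 54.1%. Simulation of the planned model gave 54% to 57%.

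**Form of the baseline term.** Both Table 7 ranges have a lower and an upper limit. The protocol synopsis also foresees low values, advising caution over dose reduction "In subjects who have undetectable androgens at baseline on their regular medication". If out-of-range values fall equally on both sides, a linear baseline term gains nothing (−0.2 to +0.2 points, simulated at 50% v 75%). The natural form is the one SAP 9.2.2 uses for the SDS, the "absolute (unsigned) number of standard deviations above or below the average of the lower and upper limit of normal", with the SD "approximated by dividing the range of the log-transformed values by four". Applied to the Table 7 limits:

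- 17-OHP: midpoint ln(1.2 × 36.4)/2 = 1.888; SD ln(36.4/1.2)/4 = 0.853
- A4, male: ln(1.4 × 5.2)/2 = 0.993; ln(5.2/1.4)/4 = 0.328
- A4, female: ln(7)/2 = 0.973; ln(7)/4 = 0.486.

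The A4 values equal Table 3, because Tables 2 and 7 share the A4 limits. The 17-OHP values do not, because the responder range is wider.

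**Change in power with that one term.** Simulated trials used 51 per arm, strata 5:3:2 with no stratum effect, a latent normal log value and a Wald test. Percentages below/above range (control, then Chronocort) were 5/45 then 5/25; 10/40 then 10/20; 20/30 then 10/20; 25/25 then 15/15. The main run had 8,000 to 12,000 trials per cell. Two shorter repeats (3,000 and 4,000 per cell) covered the first three settings.

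| Correlation, control / Chronocort | Main run (points) | Repeats (points) |
|---|---|---|
| 0.3 / 0.3 | −1.0 to −0.1 | about 0 to +0.5 |
| 0.5 / 0.5 | 0.0 to +2.1 | +0.5 to +4.0 |
| 0.7 / 0.7 | +3.8 to +7.9 | +5 to +9 |
| 0.5 / 0.2 | −1.2 to −0.4 | −0.1 to +0.7 |
| 0.7 / 0.3 | 0.0 to +1.9 | +0.9 to +3.1 |
| 0.2 / 0.5 | −0.4 to +0.2 | not run |
| 0.3 / 0.7 | +1.0 to +3.1 | not run |

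The runs differ by about a point, so the figures should be read to no finer than that.

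**Type I error.** Null rejection in the main run was 5.1% to 5.7% without the term and 5.0% to 5.5% with it.

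**Values below quantification.** SAP 9.3.3 says: "If the result at any time point is below the lower limit of quantification (LLOQ), a value of half the LLOQ will be substituted". With the lowest 10% of baseline values tied in this way, the change was −1.1 to +7.0 points over the correlations tried.

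**Model size.** Expected non-responders are 51 × 0.50 + 51 × 0.30 = 40.8. Slope terms go from three (treatment and two for strata) to four: 40.8/3 = 13.6 per term becomes 40.8/4 = 10.2.

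**The case against.** The strongest reply is that the plan already deals with this. SAP 8.2 leaves the baseline term to judgement, Protocol 13.10 gives a masked meeting the task of considering covariates, and SAP 9.3.3 records that the meeting has been held. The endpoint is supportive and has no power target. All of that stands. It makes this an optional improvement and narrows the time in which to make it.

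A second reply is that useful correlations may not occur. Under Protocol 8 (Dose Adjustment), controls keep their drugs and dosing times but may have doses changed, and both arms are titrated after weeks 4 and 12 on out-of-range values. That could weaken the link between baseline and week 24 in both arms, and the Chronocort arm also changes formulation. The main simulation had neither titration nor stratum effects. When strata explained 20% of the latent variance, the gain in the most favourable setting fell from 3.7 to 1.7 points at correlation 0.5, and from 9.3 to 7.1 at 0.7; other settings moved by about 1 point or less. This stands too, and is why a nil gain must be allowed for.

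A third reply is that the added term could lose subjects. Neither efficacy set (SAP 6.1, 6.2) requires a valid baseline profile, SAP 9.3.3 fills single time points only, and screening has no 17-OHP or A4 sample to fall back on under SAP 9.3.2. This is correct, and the fix must cover it.

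A reader might go further and infer that SAP 10.6.1 contradicts SAP 8.2. It does not: response is not a change-from-baseline variable, so the baseline term is discretionary. Nor do the documents support reading the omission as bias or loss of type I error control.

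**Conclusion.** SAP 10.6.1 is valid and within the plan's discretion. Adding one baseline term is a worthwhile low-priority change to a supportive analysis. The expected change in power is about nil, at worst a loss of about 1 point, if the correlation is weak or clearly lower in the Chronocort arm; about 0 to +3 points at 0.5, with one repeat reaching +4; and about +4 to +9 at 0.7. Response rates, correlations, allocation ratio and stratum shares are all assumed, because the documents give none of them.

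A reader might expect larger gains: with only an upper limit and 50% v 75% response, a linear term took power from 74.5% to 89.2% at correlation 0.7. Table 7 has two limits for both analytes, so that figure should not be carried over. The primary analysis, the sample size and the type I error are unaffected.

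**What to change.** Before unblinding, state in SAP 10.6.1 that:

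- the model for each analyte contains treatment, pre-baseline therapy stratum and one baseline term: the unsigned distance of the baseline 09:00 log concentration from the log midpoint of the Table 7 range, divided by a quarter of that log range (17-OHP 1.888 and 0.853; A4 as in Table 3);
- single missing or below-LLOQ baseline points are filled as in SAP 9.3.3;
- subjects with no valid baseline profile have the covariate imputed without regard to arm, for example by the mean over both arms, so that nobody is dropped;
- the adjusted response rate is obtained by standardising over the covariates.

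If allocation is already unblinded, keep the planned model and report this one as a labelled supplementary analysis.

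The cost is a few SAP sentences and a little programming, with no new data. There are three downsides. The odds ratio becomes conditional on baseline and moves away from 1 (simulated median 2.43 to 2.55 at correlation 0.5 and 2.42 to 2.86 at 0.7, with 10% below range), so it is not comparable with the unadjusted one; the standardised rates help here. One more parameter is fitted for about 41 expected non-responders. About 1 point of power may be lost if the correlation proves weak.

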**Source:**

# 17-OHP: Note the Mayo Clinic laboratory normal ranges for 17-OHP were derived from a very small number of volunteers, who did not have CAH and for whom nothing else was known, e.g. time of day, comorbidities. The appropriateness of trying to drive the CAH population into this range is questionable and therefore based on verbal feedback from clinicians who manage these patients, a broader "optimal range" has been used for 17-OHP).

\*Mayo Clinic.

A4: <http://www.mayomedicallaboratories.com/test-catalog/Clinical+and+Interpretive/9709>

The above analyses will be repeated in the full analysis set.

### 10.6.2. DEXA scans

The mean change from baseline to 24 weeks in body composition (DEXA) between the Chronocort® treatment group and the standard therapy treatment group will be compared separately for fat mass, lean mass and total bone density using an ANCOVA linear model as described in 8.2. This will be based on the efficacy evaluable analysis set excluding Germany (as DEXA scans were not performed at sites in Germany).

Summary statistics will be produced for the absolute values and change from baseline in body composition (DEXA) at each visit (weeks 4, 12 and 24).

## 10.7. Other efficacy analysis

The following analyses described in this section are considered exploratory, in order to aid better understanding of the effect of Chronocort® in CAH. As such, a limited number of analyses are described to cover the key exploratory objectives outlined in the protocol and in section 2.4.

### 10.7.1. Exploratory hormonal profile analysis

The natural logarithm of the means over the partial profiles of 17-OHP and A4 at 15:00-23:00, 23:00-07:00, and 07:00-15:00 (all refer to actual clock time of sampling) for week 24.

The natural logarithm of the mean SDS profile will be calculated in the same way as described in Section 9.2.2, with the first and last observations weighted half compared with the others.

The primary endpoint measure (natural logarithm of the 24 hour 17-OHP profile) will also be presented for the profiles measured at 4 and 12 weeks for the purposes of titration as described in section 10.5.

The ANCOVA analysis for 8-hour profiles at 24 weeks and the 24-hour profiles at 4 and 12 weeks will be conducted following the method described in Section 10.5. These analyses will be repeated for the separate pre-baseline strata.

### 10.7.2. Bone markers and laboratory assessments of special interest

Changes relative to standard treatment in:

- a. Bone markers – serum CTX and osteocalcin (after fasting)
- b. hsCRP
- c. Assessment of glucose and insulin in the morning (after fasting)
- d. Assessment of HbA1c, total testosterone, and PRA in the morning

For the assessment of glucose and insulin, the homeostasis model assessment of insulin resistance (HOMA-IR) value (Wallace TM, 2004) will be calculated using fasting values with following formula:

$$\text{HOMA-IR} = [\text{glucose (mmol/L)} * \text{insulin (}\mu\text{U/mL)}] / 22.5.$$

Change from baseline will be calculated at each visit (Week 4, Week 12, and Week 24) and summary statistics will be presented for both absolute values and change from baseline for all bone markers and laboratory assessments of special interest listed above by treatment group, pre-baseline standard therapy and visit. Shift tables of baseline to minimum and maximum on-treatment will be produced for the appropriate parameters displaying the number and percentage of subjects in each of the categories (High, Low and Normal) relative to the category of their baseline assessment. Results considered clinically significant by the investigator will be summarised. Detailed listings will be produced for all bone markers and laboratory assessments of special interest. In addition, boxplots of change from baseline over time for each bone marker or laboratory assessment of special interest will be produced along with a line connecting the mean change through time.

